14.2 Sample size and power considerations

The primary outcome is major erythroid response. A maximum of 52 patients will be enrolled into the study. An early stopping rule for lack of efficacy will be implemented as follows based on Simon's optimal two-stage design. After the first 25 patients have been enrolled and evaluated for response, the trial will be terminated early if fewer than 7 patients respond to treatment. If 7 or more responses are observed, the trial will continue until a total of 52 patients have been evaluated. At the end of the trial, the treatment will be considered efficacious and worthy of further study if 17 or more patients respond out of 52 patients.

The target response rate is assumed to be 40%. (Conservative estimate) A response rate less than 25% is considered to be clinically unimportant(21). Under these assumptions, the design specified above has the following operating characteristics. The probability of accepting the treatment for further study if the response rate is unacceptably low

(<25%) is at most 10%. In contrast, there is a 80% probability of accepting the treatment for further study if the response rate is at least 40%. The expected sample size is 32.4 subjects. It is also assumed that 10-20% of patients with plts > 50,000 that receive Len may not need Eltrombopag at all as there plts will not fall below 50,000.

Furthermore, since we will accrue patients with both high and low platelet counts, it is possible that the response rates to Lenalidomide will be different in these groups. These will be analyzed by exploratory studies.

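### The stage-1 stopping cut-off in Section 14.2 is off by one: as written, the design has type I error 11.8% and expected size 36.9, not the stated at most 10% and 32.4.

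*Combined protocol and SAP*

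**What the plan says.** Section 14.2 (Sample size and power considerations) names the method: "An early stopping rule for lack of efficacy will be implemented as follows based on Simon's optimal two-stage design". The rule is then given in three steps.

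- Interim, once 25 patients have been assessed: "the trial will be terminated early if fewer than 7 patients respond to treatment".
- Continuation: "If 7 or more responses are observed, the trial will continue until a total of 52 patients have been evaluated".
- Final: "the treatment will be considered efficacious and worthy of further study if 17 or more patients respond out of 52 patients".

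The null response rate is 25% and the target rate 40%. For the design so specified, the section claims a probability of at most 10% of accepting a regimen with an unacceptably low response rate and an 80% probability of accepting one at the target rate. It adds: "The expected sample size is 32.4 subjects".

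The stop and continue sentences agree with each other, so the written boundary is unambiguous: 6 responses stop the trial and 7 continue it. No other section gives a different cut-off. Section 12.1 says only that data are analysed after 25 patients are enrolled, and Section 13 gives the monitoring board a general interim review without a number.

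**The concern.** A Simon design is normally tabulated as two pairs, r1/n1 and r/n. The trial stops if r1 **or fewer** of n1 respond, and the regimen is rejected if r **or fewer** of n respond. Turned into wording for success, r becomes r + 1 or more; turned into wording for stopping, r1 stays r1 or fewer. Here the final limit looks correctly converted (16 became 17 or more), but the interim limit of 7 appears to have become fewer than 7. That puts a result of exactly 7 of 25 on the wrong side of the boundary.

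If so, the section's error rate, power and expected size do not describe the rule beside them. The type I error limit would be breached, and an ineffective regimen would reach stage 2 more often than planned. With exactly 7 responses, the monitoring board would hold a rule that says continue and operating characteristics that assume stopping.

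**Working it through.** **Inputs, all from Section 14.2.** Stage 1 has n1 = 25 patients and the maximum is n = 52, so stage 2 has 27. Final success needs 17 or more of 52. Null rate p0 = 0.25; target rate p1 = 0.40. Stated properties: type I error at most 0.10, power 0.80, expected size 32.4.

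**Formulas.** Let X1 ~ Bin(25, p) and X2 ~ Bin(27, p), independent, and let r1 be the largest stage-1 count that stops the trial.

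- Probability of early stopping: PET(p) = P(X1 ≤ r1).
- Probability of acceptance: A(p) = Σ over x > r1 of P(X1 = x) × P(X2 ≥ 17 − x). Type I error is A(0.25); power is A(0.40).
- Expected size: EN(p) = 25 + [1 − PET(p)] × 27.

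**Step 1: find the rule behind the stated figures.** With r1 = 7 (stop at 7 or fewer):

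- PET(0.25) = 0.7265
- Type I error = 0.0992
- Power = 0.8003
- EN(0.25) = 25 + 0.2735 × 27 = 32.38

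All three stated figures are reproduced.

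**Step 2: the rule as written.** With r1 = 6 (stop at fewer than 7):

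- PET(0.25) = 0.5611
- Type I error = 0.1179
- Power = 0.8556
- EN(0.25) = 25 + 0.4389 × 27 = 36.85

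None of the three stated figures is reproduced.

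| | Stated | As written (stop at ≤ 6) | Stop at ≤ 7 |
|---|---|---|---|
| Type I error at 25% | at most 10% | 11.79% | 9.92% |
| Power at 40% | 80% | 85.6% | 80.0% |
| Early stopping at 25% | not stated | 56.1% | 72.7% |
| Early stopping at 40% | not stated | 7.4% | 15.4% |
| Expected size at 25% | 32.4 | 36.9 | 32.4 |

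**Step 3: where the difference arises.** The two rules differ only when X1 = 7.

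- At 25%: P(X1 = 7) = 0.7265 − 0.5611 = 0.1654. On that path success needs 10 or more of the next 27. The added type I error is 0.1179 − 0.0992 = 0.0187, so the chance of success on that path is 0.0187 / 0.1654, about 11%. The added expected size is 0.1654 × 27 = 4.47 patients, which is 36.85 − 32.38.
- At 40%: P(X1 = 7) = 0.1536 − 0.0736 = 0.0800, and the added power is 0.8556 − 0.8003 = 0.0553.

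**Step 4: is 7/25, 16/52 the named design?** A search over total sizes from 20 to 69, with type I error at most 10% and power at least 80%, gives r1/n1 = 7/25 and r/n = 16/52 as the design with the smallest expected size under the null (32.38). That is Simon's optimal design.

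**Step 5: could another pair of cut-offs explain the figures?** Stopping at ≤ 5, 6, 7 or 8 was crossed with success at ≥ 16, 17, 18 or 19 of 52. Of the 16 pairs, only stopping at ≤ 7 with success at ≥ 17 gives all three stated figures together. Stopping at ≤ 6 with success at ≥ 18 meets the error limits (type I error 7.25%, power 80.1%), but its expected size is 36.85, not 32.4.

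**The case against.** The strongest points on the other side are these.

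- **Power is not harmed.** This stands. A regimen at 40% is accepted with probability 85.6%, above the stated 80%. What fails is the type I error limit and the expected size.
- **The excess is small for a single-arm phase II trial.** It is about 1.9 percentage points of type I error and about 4.5 expected patients. A positive result leads only to further study, and the maximum of 52 is unchanged. This is fair on size, but the limit breached is the plan's own. The effect on early stopping is larger: continuation at 25% rises from 27.3% (1 − 0.7265) to 43.9% (1 − 0.5611), about 1.6 times.
- **The null is worded as a rate below 25%.** At 24% the written rule does give 8.8%. But the error approaches 11.8% as the rate nears 25%, so a limit of at most 10% over that whole range still fails.
- **Futility rules are often treated as non-binding.** That makes it worse. With no interim stop, 17 or more of 52 has type I error 13.2%. The 10% limit depends on stopping at 7.
- **The expected size might be meant at the target rate.** At 40% it is 50.0 as written and 47.9 with stopping at 7 or fewer. Neither is 32.4.

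**Conclusion.** The concern holds. The interim cut-off in Section 14.2 is one response too lenient for the operating characteristics stated beside it. The written rule has type I error 11.8% against a stated limit of 10%, and expected size 36.9 against 32.4. Its power is 85.6% against the stated 80%. Exactly 7 of 25 responses has a 16.5% probability when the true rate is 25%. In that event the written rule enrols 27 further patients, whereas the Simon design behind the stated figures would stop.

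The calculation assumes independent patients with a common response probability, a one-sided exact binomial test, all 52 patients evaluable, a binding interim rule, and expected size taken under the null rate, as is usual for a Simon design. It needs no figure from outside Section 14.2. That the cause was a slip in converting r1 = 7 is an inference, but it accounts for every stated number. Because this is the plan's only efficacy decision rule, it must be corrected.

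**What to change.** Amend Section 14.2 to stop if 7 or fewer of the first 25 patients respond and to continue to 52 if 8 or more respond. Keep 17 or more of 52 as the success criterion. Every stated figure then becomes correct.

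If the sponsor prefers to continue at 7 responses, raise the final criterion to 18 or more of 52 and restate the properties: type I error 7.2%, power 80.1%, expected size 36.9.

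**Cost.** The preferred change needs no extra patients. Compared with the written rule, power falls from 85.6% to 80.0%, and the chance of stopping a truly 40% regimen at stage 1 rises from 7.4% to 15.4%. The stated 80% power already includes both. The amendment still needs the principal investigator's agreement, review by both study supporters and ethics approval under Section 15.2.

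**Timing.** The documents do not show whether stage 1 is complete. Either change should be made only before the stage-1 response count is known, because moving a cut-off afterwards would be data-dependent. If the count is already known, leave the rule as it was applied and report its true properties: type I error 11.8%, power 85.6%, expected size 36.9.

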15 REGULATORY CONSIDERATIONS

15.1 Institutional Review Board/Ethics Committee approval

The protocol for this study has been designed in accordance with the general ethical principles outlined in the Declaration of Helsinki. The review of this protocol by the IRB/EC and the performance of all aspects of the study, including the methods used for obtaining informed consent, must also be in accordance with principles enunciated in the declaration, as well as ICH Guidelines, Title 21 of the Code of Federal Regulations (CFR), Part 50 Protection of Human Subjects and Part 56 Institutional Review Boards.

The Investigator will be responsible for preparing documents for submission to the relevant IRB/EC and obtaining written approval for this study. The approval will be obtained prior to the initiation of the study.

The approval for both the protocol and informed consent must specify the date of approval, protocol number and version, or amendment number.

Any amendments to the protocol after receipt of IRB/EC approval must be submitted by the Investigator to the IRB/EC for approval. The Investigator is also responsible for notifying the IRB/EC of any serious deviations from the protocol, or anything else that may involve added risk to subjects.

Any advertisements used to recruit subjects for the study must be reviewed and approved by the IRB/EC prior to use.

15.2 Protocol amendments

Any amendment to this protocol must be agreed to by the Montefiore-Einstein Principal Investigator and reviewed by Celgene and GSK. Amendments should only be submitted to IRB/EC after consideration of Celgene and GSK review. Written verification of IRB/EC approval will be obtained before any amendment is implemented.

Each change to the protocol document must be first approved by the Einstein IRB. Amendments significantly affecting the safety of subjects, the scope of the investigation or the scientific quality of the study require additional approval by the IRB at each participating study center. A copy of the written IRB approval and corresponding documents must be provided to Montefiore-Einstein.

15.3 Continuing Review

Participating sites must submit their continuing review approval letter from their IRB of Record accompanied by the most current approved version of the consent form prior to expiration. Suspension of enrollment may be considered if receipt of this document does not occur within this time frame. Registration will be halted at any participating institution in which a current continuing approval is not on file.

15.4 Deviations and Exceptions

A protocol deviation is any change in the process or procedure of research that were not approved by amendment of an IRB approved protocol. Participating sites should report deviations to Montefiore-Einstein as soon as possible as well as maintain record the event on a deviation log that will be collected at the time of the Montefiore-Einstein's IRB continuing review.

A protocol exception on this study is defined as a planned one-time deviation from the IRB approved protocol. If a deviation from the protocol is proposed for a potential or existing participant at Montefiore-Einstein or a participating site, approval from Montefiore-Einstein IRB is required prior to the action. Participating sites should contact the Montefiore-Einstein PI who will in turn seek approval from the Montefiore-Einstein IRB.

Participating sites should report deviations and exceptions to their institution's IRBs as soon as possible per that site's institutional guidelines. Approvals/acknowledgments from the participating site IRB for protocol deviations and exceptions should be submitted to Montefiore-Einstein as received.

15.5 Informed consent

The Investigator must obtain informed consent of a subject or his/her designee prior to any study related procedures as per GCPs as set forth in the CFR and ICH guidelines.

Documentation that informed consent occurred prior to the subject's entry into the study and the informed consent process should be recorded in the subject's source documents. The original consent form signed and dated by the subject and by the person consenting the subject prior to the subject's entry into the study, must be maintained in the Investigator's study files.

15.6 Subject confidentiality

Celgene affirms the subject's right to protection against invasion of privacy. In compliance with United States federal regulations, Celgene and GSK require the Investigator to permit representatives of Celgene Corporation and GlaxoSmithKline, and when necessary, representatives of the FDA or other regulatory authorities to review and/or copy any medical records relevant to the study in accordance with local laws.

Should direct access to medical records require a waiver or authorization separate from the subject's statement of informed consent, it is the responsibility of the Investigator to obtain such permission in writing from the appropriate individual.

15.7 Study records requirements

The Investigator must ensure that the records and documents pertaining to the conduct of the study and the distribution of the protocol therapy, that is copies of CRFs and source documents (original documents, data, and records [e.g., hospital records; clinical and office charts; laboratory notes; memoranda; subject's diaries or evaluation checklists; SAE reports, pharmacy dispensing records; recorded data from automated instruments; copies or transcriptions certified after verification as being accurate copies; microfiches; photographic negatives, microfilm, or magnetic media; x-rays; subject files; and records kept at the pharmacy, at the laboratories, and at medico-technical departments involved in the clinical study; documents regarding subject treatment and drug accountability; original signed informed consents, etc.]) be retained by the Investigator for as long as needed to comply with national and international regulations (generally 2 years after discontinuing clinical development or after the last marketing approval). The Investigator agrees to adhere to the document/records retention procedures by signing the protocol.

15.8 Premature discontinuation of study

The Principal Investigator, institution, GSK and Celgene have the right to discontinue this study at any time for reasonable medical or administrative reasons. Possible reasons for termination of the study could be but are not limited to:

- Unsatisfactory enrollment with respect to quantity or quality.
- Inaccurate or incomplete data collection.
- Falsification of records.
- Failure to adhere to the study protocol.

Any possible premature discontinuation would be documented adequately with reasons being stated, and information would have to be issued according to local requirements (e.g., IRB/EC, regulatory authorities, etc.).

16 CORRELATIVE STUDIES:

Correlative studies will be performed on all subjects. Specifically, we will study:

a. Whole transcriptome sequencing (RNA-Seq) of MDS bone marrow progenitors and correlation with response. Pretreatment bone marrow aspirates will be used for these studies. Bone marrow stem cells will be sorted and RNA will be isolated. Sequencing libraries will be generated and subjected to massive parallel sequencing using an Illumina

HiSeq2000 instrument.. The transcriptome patterns will be correlated with response. In addition to gene expression patterns, this study will also correlate mutations and single nucleotide polymorphisms with response to lenalidomide and eltrombopag. Somatic mutations will be identified by comparison of marrow and germline (toenail clippings or cheek swabs) samples.

b. Analysis of “MDS” stem cells pre and post treatment with the combination of eltrombopag and lenalidomide and their correlation with response (Study co-chair [name] is an expert in flow sorting of leukemia stem cells and their functional characterization, both in vitro and in vivo). Using high-speed multi-parameter fluorescence-activated cell sorting we will separate bone marrow progenitors into long-term and short-term hematopoietic stem cells as well as more committed myeloid, erythroid and megakaryocytic progenitors, as performed previously (22, 23). Stem cell compartments expanded in MDS as compared to normal bone marrow will be identified. Sorted cell fractions will be studied for the presence of pathogenic mutations and characteristic chromosomal lesions. Functional validation of sorted cell populations will be performed in vitro and in vivo.

Our preliminary studies indicate that primitive stem cells (LT-HSCs and ST-HSCs) are expanded in MDS and harbor initiating karyotypic abnormalities and striking alterations in DNA methylation with an accumulation of aberrantly hypermethylated loci. Furthermore, we and others observe that karyotypically abnormal stem cells persist in the bone marrow even after morphological complete remission and thus may potentially lead to relapse of MDS (24). These preliminary data lead us to hypothesize that a pool of disease-initiating stem or early progenitor cells exists in MDS that contains and progressively acquires genetic and epigenetic alterations and may persist after conventional treatments. The study of these MDS cells-of-origin and MDS-initiating cell populations will reveal fundamentally new information about early pathogenic events, which represent particularly promising targets for therapeutic intervention, as well as the modes of MDS progression.

Quantitative and cytogenetic assessment of MDS stem and progenitor cells from marrow samples of responders and non-responders to lenalidomide and eltrombopag will be performed. Karyotypic, transcriptomal, as well as methylomic analysis of these cells will be conducted for clonal genetic and epigenetic assessment. Comparison of pretreatment and post treatment samples from both subsets of patients will demonstrate whether a decrease in clonal stem cells correlates with clinical response. We will also determine whether persistence of clonal stem cells in responders correlates with a risk of future relapse.

The use of lenalidomide in pregnant females and nursing mothers has not been studied nor has the effect of the lenalidomide on human eggs and sperm. Lenalidomide is structurally related to thalidomide. Thalidomide is a known human teratogenic active substance that causes severe life-threatening birth defects. An embryofetal development study in animals indicates that lenalidomide produced malformations in the offspring of female monkeys who received the drug during pregnancy. The teratogenic effect of lenalidomide in humans cannot be ruled out. Therefore, a risk minimization plan to prevent pregnancy must be observed.

All study participants must be registered into the mandatory Revlimid REMS™ program, and be willing and able to comply with the requirements of Revlimid REMS™.

Criteria for females of childbearing potential (FCBP)

This protocol defines a female of childbearing potential as a sexually mature female who: 1) has not undergone a hysterectomy or bilateral oophorectomy or 2) has not been naturally postmenopausal for at least 24 consecutive months (i.e., has had menses at any time in the preceding 24 consecutive months).

The investigator must ensure that:

- Females of childbearing potential comply with the conditions for pregnancy risk minimization, including confirmation that she has an adequate level of understanding
- Females NOT of childbearing potential acknowledge that she understands the hazards and necessary precautions associated with the use of lenalidomide
- Male patients taking lenalidomide acknowledge that he understands that traces of lenalidomide have been found in semen, that he understands the potential teratogenic risk if engaged in sexual activity with a female of childbearing potential, and that he understands the need for the use of a condom even if he has had a vasectomy, if engaged in sexual activity with a female of childbearing potential.

Contraception

Females of childbearing potential (FCBP) enrolled in this protocol must agree to use two reliable forms of contraception simultaneously or to practice complete abstinence from

heterosexual intercourse during the following time periods related to this study: 1) for at least 28 days before starting lenalidomide; 2) throughout the entire duration of lenalidomide treatment; 3) during dose interruptions; and 4) for at least 28 days after lenalidomide discontinuation.

The two methods of reliable contraception must include one highly effective method and one additional effective (barrier) method. FCBP must be referred to a qualified provider of contraceptive methods if needed. The following are examples of highly effective and additional effective methods of contraception:

- Highly effective methods:
 - Intrauterine device (IUD)
 - Hormonal (birth control pills, injections, implants)
 - Tubal ligation
 - Partner's vasectomy
- Additional effective methods:
 - Male condom
 - Diaphragm
 - Cervical Cap

Because of the increased risk of venous thromboembolism in patients with multiple myeloma taking lenalidomide and dexamethasone, combined oral contraceptive pills are not recommended. If a patient is currently using combined oral contraception the patient should switch to one of the effective method listed above. The risk of venous thromboembolism continues for 4–6 weeks after discontinuing combined oral contraception. The efficacy of contraceptive steroids may be reduced during co-treatment with dexamethasone.

Implants and levonorgestrel-releasing intrauterine systems are associated with an increased risk of infection at the time of insertion and irregular vaginal bleeding. Prophylactic antibiotics should be considered particularly in patients with neutropenia.

Pregnancy testing

Medically supervised pregnancy tests with a minimum sensitivity of 50 mIU/mL must be performed for females of childbearing potential, including females of childbearing potential who commit to complete abstinence, as outlined below.

Before starting lenalidomide

Female Patients:

FCBP must have two negative pregnancy tests (sensitivity of at least 50 mIU/mL) prior to prescribing lenalidomide. The first pregnancy test must be performed within 10-14 days prior to prescribing lenalidomide and the second pregnancy test must be performed within 24 hours prior to prescribing lenalidomide. The patient may not receive lenalidomide until the Investigator has verified that the results of these pregnancy tests are negative.

Male Patients:

Must agree to practice complete abstinence or agree to use a condom during sexual contact with pregnant females or females of childbearing potential throughout the entire duration of lenalidomide treatment, during dose interruptions and for at least 28 days following lenalidomide discontinuation, even if he has undergone a successful vasectomy.

During study participation and for 28 days following lenalidomide discontinuation*Female Patients:*

- FCBP with regular or no menstrual cycles must agree to have pregnancy tests weekly for the first 28 days of lenalidomide treatment, including dose interruptions and then every 28 days throughout the remaining duration of lenalidomide treatment, including dose interruptions, at lenalidomide discontinuation, and at Day 28 following lenalidomide discontinuation. If menstrual cycles are irregular, the pregnancy testing must occur weekly for the first 28 days of lenalidomide treatment, including dose interruptions, and then every 14 days throughout the remaining duration of lenalidomide treatment, including dose interruptions, at lenalidomide discontinuation, and at Day 14 and Day 28 following lenalidomide discontinuation.
- At each visit, the Investigator must confirm with the FCBP that she is continuing to use two reliable methods of birth control at each visit during the time that birth control is required.
- If pregnancy or a positive pregnancy test does occur in a study patient, lenalidomide must be immediately discontinued.
- Pregnancy testing and counseling must be performed if a patient misses her period or if her pregnancy test or her menstrual bleeding is abnormal. Lenalidomide treatment must be temporarily discontinued during this evaluation.

- Females must agree to abstain from breastfeeding during study participation and for at least 28 days after lenalidomide discontinuation.

Male Patients:

- Must practice complete abstinence or use a condom during sexual contact with pregnant females or females of childbearing potential throughout the entire duration of lenalidomide treatment, during dose interruptions and for at least 28 days following lenalidomide discontinuation, even if he has undergone a successful vasectomy.
- If pregnancy or a positive pregnancy test does occur in the partner of a male study patient during study participation, the investigator must be notified immediately.

Additional precautions

- Patients should be instructed never to give lenalidomide to another person.
- Female patients should not donate blood during therapy and for at least 28 days following discontinuation of lenalidomide.
- Male patients should not donate blood, semen or sperm during therapy or for at least 28 days following discontinuation of lenalidomide.
- Only enough lenalidomide for one cycle of therapy may be prescribed with each cycle of therapy.

